#### **4.2.25.3 Handling of Dropouts and Missing Data**

Participants who experience all-cause death, or loss to follow-up prior to days 90 and 180 respectively will be excluded from the numerator and denominator of the analysis.

#### **4.2.25.4 Primary Analysis of Exploratory Endpoint #17**

The number and proportion of participants requiring RAASi at days 90 and 180 by treatment arm will be summarised.

#### **4.2.25.5 Additional Analyses of the Exploratory Endpoint #17**

Not Applicable.

#### **4.2.25.6 Subgroup Analyses**

Not Applicable.

### **4.3 Pharmacodynamic Endpoint(s) (if not already covered as endpoint variables)**

#### **4.3.1 Analysis**

Not Applicable.

#### **4.3.2 Definitions and Derivations**

Not Applicable.

#### **4.3.3 Presentation**

Not Applicable.

### **4.4 Pharmacokinetics (if not already covered as endpoint variables)**

Not Applicable.

### **4.5 Immunogenicity (if applicable and if not already covered as endpoint variables)**

Not Applicable.

### **4.6 Safety Analyses (if not already covered as endpoint variables)**

The domain safety covers exposure, adverse events, clinical laboratory, vital signs, and ECG.

Tables are provided for the SSO and the SSR, listings are provided for All participants or the safety set depending on the availability of data.

## **4.6.1      Exposure**

### **4.6.1.1    Definitions and Derivations**

Exposure (i.e. duration of treatment) will be defined as follows:

Total (or intended) exposure of study treatment

- Total (or intended) exposure = min (last dose date where dose > 0g, date of death, date of discontinuation) – first dose date + 1

The dosage (g/day) will be calculated for the inpatient period and outpatient period respectively:

The total cumulative dose received (g)/Number of days receiving study drug (i.e. excluding dose interruptions)

### **4.6.1.2    Presentation**

Actual and total exposure (days) will be summarised in total for the SSO and by treatment group for the SSR by the following: mean, standard deviation, minimum, maximum, median and number of observations.

SZC (g/day) will be summarised in total for the SSO and by treatment group for the SSR by the following: range of dose for any participant, mean dose, range of mean doses, median dose, interquartile range of dose. Total cumulative dose received (g) will be summarised by mean and range. The range of the maximum dose received (g/day) will be summarised. For each study visit period (e.g. from visit 1 to visit 2, visit 2 to visit 3) the total number (%) of participants who received dose will be presented and the prescribed daily dose.

## **4.6.2      Adverse Events**

### **4.6.2.1    Definitions and Derivations**

All Adverse events, (non-serious and serious adverse events (SAEs) will be collected from time of signature of the informed consent form, throughout the treatment period including during the follow-up period. A treatment emergent AE (TEAE) will be defined as an AE with the start date on or after the first dose date during the inpatient period up to (and including) 7 days after the last dose date, and events with start date prior to the date of first dose of study treatment whose severity worsens on or after the date of first dose during the inpatient period.

TEAEs will be further categorised as either (i) occurring during the inpatient period, if the start date is on or after the first dose date during the inpatient period and prior to the date of randomization, (ii) occurring during the outpatient period if the start date is on or after the date of randomization and prior to the date of study treatment discontinuation+7.

MedDRA [Version 24.1 (or a later version if updated during the study)] will be used to classify AEs system organ class (SOC) and preferred term (PT).

Every effort should be made to collect the maximum intensity and relationship to treatment for all AEs. However, if the maximum intensity is missing for a TEAE then it will be considered as severe only in the overall category in the summary tables. If the relationship to treatment is missing, then the AE will be considered as possibly related to treatment.

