
• To assess the safety and tolerability of SZC compared to SoC	
Safety and tolerability will be evaluated in terms of AEs, vital signs, clinical safety laboratory, and ECG.
 
• Population: Safety set open and safety set randomised• Endpoint: Assessments related to AEs cover:
- Occurrence/frequency- Relationship to SZC as assessed by investigator- Intensity- Seriousness- Death- AEs leading to discontinuation of SZC.• Intercurrent event strategy: Discontinuation of treatment and use of rescue therapy for HK will follow the treatment policy strategy (ie, regardless of the intercurrent event).• Population level summary (analysis): Categorical summary by treatment group as received.

Exploratory	

• To evaluate the effect of continuing SZC as part of the discharge medications, compared to SoC, in reducing the incidence of the composite outcome of hospital admissions or ED visits with HK as a contributing factor or all-cause death	
• Population: Full analysis set• Endpoint: Time to first occurrence of any component of hospital admission or ED visit, both with HK as a contributing factor, or all-cause death at any time post-discharge up to 180 days.• Intercurrent event strategy: Participants who discontinue treatment, use rescue therapy for HK, or require hospital admissions or ED visits without HK as a contributing factor will continue to be followed up to the first component of the composite endpoint (treatment policy strategy). Participants who are lost to follow-up will be censored at their date of loss to follow-up. Participants who die of any cause will be considered an event (composite variable strategy). Participants who have RAASI down-titration (including discontinuation) will continue to be followed up to the first component of the composite endpoint (treatment policy strategy).• Population level summary (analysis): Kaplan-Meier plots of the survival function for the SZC and SoC treatment groups will be presented. Log-rank test for testing will be used to calculate a two-sided p-value, Cox proportional hazards ratio for estimation, with randomised treatment group as the independent variable. The HR and the two-sided 95% confidence interval will be presented. The risk difference and two-sided 95% confidence interval will be presented.

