9.4.4 Safety

Safety will be assessed in terms of AEs, SAEs, AEs leading to treatment discontinuation, clinical laboratory data, vital signs, and ECG. Appropriate summaries of these data will be presented by treatment group.

Adverse events will be classified using the Medical Dictionary for Regulatory Activities system organ class (SOC) and PT. A treatment-emergent AE (TEAE) is defined as an AE with the start date on or after the first dose date and up to (and including) 7 days after the last dose date. Only TEAEs will be included in table summaries.

Adverse events will be presented for each treatment group by SOC, and PT covering number and percentage of participants reporting at least 1 event and number of events where appropriate.

An overview of AEs will present for each treatment group the number and percentage of participants with any AE, AEs with outcome of death, SAEs, and AEs leading to discontinuation of IMP.

Separate AE tables will be provided taken into consideration relationship as assessed by the investigator, maximum intensity, seriousness, death, and events leading to discontinuation of IMP.

Key participant information will be presented for participants with AEs with outcome of death, SAEs, and AEs leading to discontinuation of IMP.

An AE listing for the safety analysis set will cover details for each individual AE; an AE listing for participants who were not exposed to IMP is presented separately.

Full details of AE analyses will be provided in the SAP.

An overview of oedema-related AEs and instances of $K^+ < 3.5$ will be presented.

All AE data will be listed for all participants. In addition, SAEs and AEs that led to withdrawal or death and treatment-related AEs will be listed.

Clinical safety laboratory assessments will be summarised and listed. Shift tables will be provided for select tests, where shift from screening baseline to the worst value within each part of the study and overall will be summarised. Laboratory data outside the reference ranges will be indicated in all listings.

All safety analyses will be performed on the SSO and SSR. In general, safety assessments will be reported descriptively by treatment group. Full details on safety analyses will be provided in the SAP.

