### 4.6.2.2 Presentation

#### AE Summary

An overall summary table of the number of participants experiencing each category of AEs will be produced using the SSO and SSR. Analyses using the SSO will be restricted to AEs which occurred during the inpatient period and will be presented overall. Analyses using the SSR will include all AEs and will be presented by treatment group received during the outpatient period and overall.

Any AE occurring within 7 days of the discontinuation of investigational product will be included in the AE summaries. Treatment emergent adverse events (TEAEs) occurring prior to first dose of investigational product (i.e. before study day 1) which subsequently worsen in severity following dosing will be presented in the summary tables. All other AEs occurring prior to first dose of investigational product (i.e. before study day 1) or more than 7 days after the discontinuation of investigational product will be listed separately, but not included in the summaries.

An overview table will summarize the number and percentage of participants with at least one of the following AEs, where participants with more than one AE in a particular category are counted only once in that category, as well as the absolute counts of number of AEs. In the overall summary table for the SSO, no event rate will be displayed. In the overall summary table for the SSR, the event rate, per 100 patient years, will be displayed. This will be calculated as the number of participants with at least one AE (in either inpatient or outpatient phase) divided by the total time at risk (i.e. time from first dose of SZC during the inpatient phase to date of study discontinuation) across all participants in given group, multiplied by 365.25 multiplied by 100.

- Any AEs
- Any AEs with outcome of death
- Any SAEs (including events with outcome of death)

- Any AEs leading to treatment discontinuation

Number of participants with AEs

The number and percentage of participants reporting each AE and the absolute count of AEs will be summarised by system organ class (SOC) and preferred term (PT). Tables will be sorted by international order for SOC and PTs will be sorted alphabetically. The following summaries will be produced using the SSO and SSR:

- AEs;
- Most common AEs (>5% in any treatment group);
- AEs by relationship to treatment;
- AEs by maximum intensity;
- AEs leading to treatment discontinuation;
- SAEs;
- SAEs related to treatment;
- AEs leading to death;

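### The SZC versus SoC adverse-event tables use a treatment-tied cut-off that is never defined for Arm B, so the tabulated follow-up is unequal by arm on either reading

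*SAP*

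**What the plan says.** **Cut-off for the tables.** SAP 4.6.2.1 defines a treatment-emergent AE (TEAE) as one that starts "on or after the first dose date during the inpatient period up to (and including) 7 days after the last dose date". Protocol 9.4.4 has the same 7-day limit and adds: "Only TEAEs will be included in table summaries". For the outpatient category, SAP 4.6.2.1 requires a start "prior to the date of study treatment discontinuation+7". SAP 4.6.2.2 then says that AEs occurring "more than 7 days after the discontinuation of investigational product will be listed separately, but not included in the summaries".

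**Scope of the by-arm tables.** SAP 4.6.2.2 restricts the Safety Set Open (SSO) to inpatient AEs and continues: "Analyses using the SSR will include all AEs", where SSR is the Safety Set Randomised. The SSR event rate divides by "time from first dose of SZC during the inpatient phase to date of study discontinuation".

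**Estimand.** The safety row of Protocol Table 3 states: "Discontinuation of treatment and use of rescue therapy for HK will follow the treatment policy strategy (ie, regardless of the intercurrent event").

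**Treatment and follow-up.** Arm B is discharged without SZC and has SoC until end of treatment (EOT) at 180 days (Protocol 6.2). Participants who permanently stop study intervention stay in follow-up (Protocol 7.1.1), and AEs are collected in both arms through the follow-up period (Protocol 8.3.1).

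**The concern.** A cut-off of last dose plus 7 days works when both arms take a study drug with a recorded last dose. Here one arm is SoC without SZC at discharge, and neither document says which date closes its window. The text supports two answers, and they distort the comparison in opposite directions.

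- **SZC reading.** SoC AEs, SAEs and fatal AEs after about the first week at home drop out of the tables, while the same events on SZC are counted. With similar true rates, SZC looks worse.
- **SoC reading.** AEs after an early SZC stop drop out of Arm A, while Arm B is counted throughout. With similar true rates, SZC looks somewhat better.

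Neither fits an estimand that ignores discontinuation and rescue. Both also set a truncated count over a denominator that keeps running to study discontinuation. In an open-label trial this choice should be written down, not left to programming.

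**Working it through.** The plan gives no figure on this point, so there is none to reproduce. The check compares passages and counts days.

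**Step 1: what is the last dose in Arm B?**

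Text pointing to SZC only:
- SZC is the only product in Protocol Table 5, and only Arm A is dispensed study intervention after discharge (Schedule of Activities, footnote k).
- SAP 3.3.2 equates EOT with the last SZC dose, and SAP 3.3.1 starts the follow-up phase the day after it.
- SAP 4.6.1.1 uses the last dose date for a dose in grams: "min (last dose date where dose > 0g, date of death, date of discontinuation").
- SAP 4.6.2.2 words its exclusion in terms of investigational product.

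Text pointing to SoC as study treatment until EOT:
- Protocol 4.2 and 6.6 call SoC a study intervention, and Protocol 6.2 runs it to Day 180.
- The Amendment 3 rationale links the 7 days to the visit 7 days after EOT.
- SAP 4.1.1.2 summarises treatment completion and discontinuation by treatment group without limiting this to Arm A. SAP 4.1.8 refers to a first outpatient dose of study treatment and tabulates by arm.

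No passage settles it, and there is no accountability for SoC (Protocol 6.6).

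**Step 2: tabulated days after randomisation.** Window = stop day + 7. Assumptions: follow-up to Day 180 + 7 = 187, and no SZC after discharge in Arm B.

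| Reading | Arm B | Arm A, stop Day 30 | Arm A, stop Day 90 | Arm A, stop Day 180 |
|---|---|---|---|---|
| SZC | 0 + 7 = 7 | 37 | 97 | 187 |
| SoC | 180 + 7 = 187 | 37 | 97 | 187 |
| Actually followed | 187 | 187 | 187 | 187 |

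**Step 3: count against denominator.** The SSR rate starts at the first inpatient dose, so add an inpatient stay of L days (1 to 21). The denominator per participant is L + 187.

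- SZC reading, window ratio for an Arm A completer against Arm B, (L + 187)/(L + 7): 188/8 = 23.5 for L = 1; 194/14 = 13.9 for L = 7; 208/28 = 7.4 for L = 21.
- SZC reading, share of the Arm B denominator in which no AE can be tabulated, 180/(L + 187): 95.7%, 92.8% and 86.5% for the same stays.
- Both readings, the same share for an Arm A early stopper: Day 30, 150/(L + 187) = 79.8% to 72.1%; Day 90, 90/(L + 187) = 47.9% to 43.3% (L = 1 to 21).

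**Step 4: illustration.** The documents give no AE risk and no SZC-stop rate, so these are assumptions.

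- SoC reading. If a fraction d of Arm A stops on day s, the untabulated share of Arm A post-randomisation time is d(180 − s)/187. With s = 90 it is 4.8%, 9.6% and 14.4% for d = 10%, 20% and 30%. Over s = 30 to 150 and d = 10% to 30% it ranges from 1.6% to 24.1%.
- SZC reading. With a constant hazard h = −ln(1 − p)/187, the post-discharge Arm B risk shown is 1 − exp(−7h). For p = 40%, 60% and 80% to Day 187 the tables would show 1.9%, 3.4% and 5.8%.

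**The case against.** The best defence is that the SZC reading is unlikely to be what was meant. The EOT-based rationale, the SoC wording and the by-arm disposition tables suggest that a sensible programmer would use EOT + 7 for Arm B. The denominator then fits Arm B and Arm A completers to within the visit window, leaving only early SZC stoppers mismatched. This largely stands: the 7 against 187 days is what the text allows, not what it clearly prescribes. It also applies only to Arm B participants never given SZC after discharge, since Protocol 6.2 permits a K-binder from Day 7. But no passage states the EOT rule, and it still truncates early stoppers in Arm A alone.

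A reader might infer three competing windows, taking "Analyses using the SSR will include all AEs" as a third with no cut-off. The documents do not support that firmly. The preceding sentence limits the SSO to inpatient AEs, and the SAP makes the same SSO/SSR contrast for laboratory tests, vital signs and ECG. The phrase probably means inpatient plus outpatient AEs. It should be clarified, but it is not a clear third rule.

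A reader might also infer that an AE starting exactly on day 7 falls between the inclusive limit and "prior to the date of study treatment discontinuation+7". That holds only if the discontinuation date equals the last dose date, which the SAP does not say. Such an AE would remain a TEAE and lack only a period label.

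Finally, last dose + 7 is the protocol's own rule, so the conflict with Table 3 lies partly within the protocol. That is right, and it is why both documents need reconciling.

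**Conclusion.** The point holds. The by-arm AE tables have a treatment-tied cut-off with no stated date for Arm B. Both supportable readings give unequal windows, conflict with the treatment-policy safety estimand, and leave a count that does not match its denominator.

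The size depends on the reading. On the SZC reading it is large: about 7 against 187 days, for Arm B participants without SZC after discharge. On the SoC reading it is modest and confined to Arm A early stoppers; it would vanish if nobody stopped early. The day counts assume complete follow-up to about Day 187.

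This should be fixed, but it does not threaten the trial's main conclusions. The AE tables are descriptive and all AEs are listed. All-cause death and hospital admission are analysed by arm as components of efficacy endpoints. A reader might infer that SoC safety data would be lost; they would not, because AEs are collected in both arms through follow-up. Only their place in the tables is at issue.

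**What to change.** For the SSR AE tables and rates, count AEs in both arms to one end date that does not depend on SZC dosing: the last follow-up assessment, consent withdrawal, last contact or death, whichever comes first, as in Protocol Table 8. End time at risk on that same date. Keep the protocol's last-dose + 7 TEAE table for Arm A as supportive.

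Reconcile the texts:
- Bring Protocol 9.4.4 and SAP 4.6.2.1 and 4.6.2.2 into line with the Table 3 estimand, and state what the all-AEs sentence means.
- Align the outpatient period, which ends at EOT in SAP 3.3.1.2 but at the last follow-up assessment in Protocol Table 8.
- Use one boundary for day 7 and one anchor date.
- Record the change in SAP Section 2.

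The cost is SAP wording, one Section 2 entry and table programming. No new data are needed.

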## Deaths

All adverse events leading to death, including those not related to an AE, will be collected until the end of the study.

### 4.6.2.2 Presentation

#### AE Summary

An overall summary table of the number of participants experiencing each category of AEs will be produced using the SSO and SSR. Analyses using the SSO will be restricted to AEs which occurred during the inpatient period and will be presented overall. Analyses using the SSR will include all AEs and will be presented by treatment group received during the outpatient period and overall.

Any AE occurring within 7 days of the discontinuation of investigational product will be included in the AE summaries. Treatment emergent adverse events (TEAEs) occurring prior to first dose of investigational product (i.e. before study day 1) which subsequently worsen in severity following dosing will be presented in the summary tables. All other AEs occurring prior to first dose of investigational product (i.e. before study day 1) or more than 7 days after the discontinuation of investigational product will be listed separately, but not included in the summaries.

An overview table will summarize the number and percentage of participants with at least one of the following AEs, where participants with more than one AE in a particular category are counted only once in that category, as well as the absolute counts of number of AEs. In the overall summary table for the SSO, no event rate will be displayed. In the overall summary table for the SSR, the event rate, per 100 patient years, will be displayed. This will be calculated as the number of participants with at least one AE (in either inpatient or outpatient phase) divided by the total time at risk (i.e. time from first dose of SZC during the inpatient phase to date of study discontinuation) across all participants in given group, multiplied by 365.25 multiplied by 100.

- Any AEs
- Any AEs with outcome of death
- Any SAEs (including events with outcome of death)

- Any AEs leading to treatment discontinuation

Number of participants with AEs

The number and percentage of participants reporting each AE and the absolute count of AEs will be summarised by system organ class (SOC) and preferred term (PT). Tables will be sorted by international order for SOC and PTs will be sorted alphabetically. The following summaries will be produced using the SSO and SSR:

- AEs;
- Most common AEs (>5% in any treatment group);
- AEs by relationship to treatment;
- AEs by maximum intensity;
- AEs leading to treatment discontinuation;
- SAEs;
- SAEs related to treatment;
- AEs leading to death;

All AE data will be listed appropriately for all participants including information on AE duration, intensity, seriousness, action taken, outcome, relationship as assessed by investigator, timing of onset of AE in relation to the first dose of study treatment in the inpatient period, study treatment at the time of event.

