Assuming a 20% drop-out rate from enrolment to randomisation and a 20% drop out post-discharge (post-randomisation), approximately 163 participants will be enrolled, resulting in approximately 130 participants discharged and randomised, to achieve 104 evaluable participants (52 per arm).

Note: “Enrolled” means a participant's, or their legally acceptable representative's, agreement to participate in a clinical study following completion of the informed consent process. Potential participants who are screened for the purpose of determining eligibility for the study, but are not assigned treatment in the study, are considered “screen failures”, unless otherwise specified by the protocol.

Intervention Groups and Duration:

All participants will be treated with SZC as per local label (correction and/or maintenance treatment) during the in-hospital phase. The duration of in-hospital phase will be 1 to 21 days post-enrolment; medical monitor's approval may be sought for allowing longer duration hospital stays for specific participants.

At discharge, participants who are NK (K^+ between 3.5 and 5.0 mmol/L, inclusive) and have been started on a maintenance dose for SZC will be randomised in a 1:1 ratio to one of the following arms and subsequently enter the outpatient phase:

- Arm A: Participants discharged with SZC, as per local label, to manage HK until end of outpatient phase
- Arm B: Participants discharged with SoC, as per local practice, to manage HK until end of the study.

Note: Participants intended to receive a K-binder at discharge (as per the site routine medical practice) will not be randomised and will be discontinued from the study. Still, it is allowed that participants randomised into Arm B have any K-binder prescribed at Day 7 post-discharge (or after Day 7 post-discharge), to treat confirmed HK or in case there is an increase in K^+ level since discharge that, in the investigator's opinion, requires therapy.

The duration of outpatient phase will be approximately 180 days.

After the outpatient phase, participants will enter into the follow-up phase which will last 7 days. Study drug will be discontinued for participants in Arm A. These participants will be treated as per local practice (SoC). Participants in Arm B will continue SoC treatment.

The total study duration for each participant will then be approximately 6 months.

Adjudication Committee: Yes

Statistical Methods:

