^a Any time study drug dose is adjusted, or if in either treatment arm, a concomitant medication which may affect K⁺ levels is changed (eg, use of RAASi or diuretics), the participant needs to return to the site 7 (\pm 2) days later for a K⁺ measurement and recording of adverse events and concomitant medications.

Participants randomised to Arm B will be discharged without SZC and will receive SoC per local practice for managing their K⁺ until the EOT (180 days post-discharge). The SoC will be at the discretion of the treating physician; however, participants intended to be discharged with a K-binder will not be randomised. However, participants in Arm B may have a K-binder prescribed at Day 7 post-discharge (or after Day 7 post-discharge) to treat confirmed HK or in case there is an increase in K⁺ level since discharge that, in the investigator's opinion, requires therapy.

The K⁺ levels will be measured at on-site visits at Days 7 (local laboratory), 90 (local and central laboratories), and 180 (local and central laboratories) (see Sections 8.1.1 and 8.2.4). Overall monitoring frequency will depend upon a variety of factors including other medications, progression of CKD, and dietary K⁺ intake. It is the responsibility of the treating physicians to check the participant K⁺ as medically appropriate/in accordance with the label (for both SZC and SoC arms). In addition to the scheduled on-site visits, participants should return to the site for a local K⁺ measurement 7 (\pm 2) days after any dose adjustment to SZC.

Additionally, participants in either treatment arm should have their K⁺ measured locally 7 (\pm 2) days after changes are made to medications that affect K⁺ levels (eg, use of RAASI or diuretics).

Such additional K⁺ checks and site visits will take place as clinically indicated and the resulting data, including AEs and concomitant medication information, relating to these visits will also be collected during the study.

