### **Safety Set Randomised**

The Safety Set Randomised (SSR) will include all randomised participants receiving at least one dose of SZC after the date and time of randomisation in Arm A (SZC), and all randomised participants in Arm B (Standard of Care (SOC) according to local practice). The date and time of randomisation will be as recorded in the IRT system. Participants will be analysed according to treatment actually received. The SSR will be the analysis population used for presentations of safety information during the outpatient period.

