##### **4.6.4.2 Presentations**

Shift tables will be presented where shift from baseline to the maximum value will be summarised. These will be provided separately for the SSO, which will be limited to visits during the inpatient period, and the SSR, which will summarize the worst overall value across all visits.

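### SAP 4.6.2.2 counts adverse events from the all-SZC run-in in the by-arm safety tables, so the SoC column carries events that arose on SZC

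*SAP*

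**What the plan says.** The Protocol synopsis describes an SZC run-in for everyone: "All participants will be treated with SZC as per local label (correction and/or maintenance treatment) during the in-hospital phase". On its length it says: "The duration of in-hospital phase will be 1 to 21 days post-enrolment", with longer stays possible if the medical monitor agrees. After randomisation, Protocol 6.2 says: "Participants randomised to Arm B will be discharged without SZC".

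SAP 3.2 gives the SSR a defined purpose: "The SSR will be the analysis population used for presentations of safety information during the outpatient period". SAP 4.6.2.2 restricts the SSO tables to inpatient events but says of the SSR: "Analyses using the SSR will include all AEs and will be presented by treatment group received during the outpatient period and overall". The SSR event rate is the "number of participants with at least one AE (in either inpatient or outpatient phase) divided by the total time at risk", and that time is defined as "time from first dose of SZC during the inpatient phase to date of study discontinuation".

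SAP 4.6.2.1 splits treatment-emergent events into an inpatient and an outpatient category, the latter starting at randomisation. None of the SSR tables listed in 4.6.2.2 is restricted to the outpatient category. Both sections also stop counting events 7 days after the last dose, or after discontinuation of the investigational product.

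For urinalysis, SAP 4.6.4.2 describes the shift table for "the SSR, which will summarize the worst overall value across all visits". The QTcF categories in SAP 4.6.7.2 use each participant's maximum over the SSR's ECG visits.

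**The concern.** The safety objective is SZC compared with SoC. Events before randomisation cannot be effects of allocation, because both arms were then on the same drug. The SSR tables nevertheless place them in columns headed by outpatient treatment. An SoC participant whose only adverse event occurred on SZC in hospital is counted as an SoC participant with an adverse event. If the investigator judged it related, it also enters the SoC column of the relatedness table.

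The overview and the tables by system organ class and preferred term count participants once per category. An in-hospital event therefore also hides a later outpatient event of the same kind in the participant count. Both mechanisms pull the arms' incidences together. A reader who takes these tables as the post-discharge comparison, which is what SAP 3.2 promises, would be misled about what they contain.

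**Working it through.** The plan states no figure on this point, so there is nothing to reproduce. The check is a reading of the text, followed by illustrations on assumed rates.

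**1. Start of the window.** SAP 3.2 says outpatient. SAP 4.6.2.2 says all events, a numerator covering either phase, and time at risk from the first inpatient dose. Three separate statements in 4.6.2.2 agree, so this is not one loose phrase. It conflicts with SAP 3.2.

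**2. Effect on incidence.** Let p0 be the in-hospital incidence, the same in expectation in both arms because randomisation comes afterwards, and p1 an arm's outpatient incidence. With independent phases:

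reported incidence = 1 − (1 − p0)(1 − p1)

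The difference between arms is then (1 − p0) × (p1,SZC − p1,SoC). Without independence, the factor applies to the difference among participants with no in-hospital event. Taking outpatient incidences of 50% and 40% (both assumed; difference 10 points, ratio 1.25):

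| Assumed p0 | SZC | SoC | Difference | Ratio |
|---|---|---|---|---|
| 5% | 52.5% | 43.0% | 9.5 points | 1.22 |
| 20% | 60.0% | 52.0% | 8.0 points | 1.15 |
| 40% | 70.0% | 64.0% | 6.0 points | 1.09 |

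**3. A rarer term.** Protocol Table 2 gives oedema in 1.7% on placebo and 5.2% on SZC 10 g over up to one month. Assume these are constant 30-day hazards, that placebo stands in for SoC, and that follow-up is 180 + 7 = 187 days.

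- Outpatient only: 1 − 0.948^(187/30) = 28.3% against 1 − 0.983^(187/30) = 10.1%. The difference is 18.2 points and the ratio 2.79.
- In-hospital incidence after 1, 7 and 21 days: p0 = 1 − 0.948^(d/30) = 0.2%, 1.2% and 3.7%.
- As the SAP is written, with no early cut-off for SoC: differences of 18.1, 18.0 and 17.5 points; ratios of 2.76, 2.60 and 2.30.
- Of the SoC participants counted with oedema, 2%, 11% and 27% had it in the run-in. With 130/2 = 65 per arm, that is about 0.1, 0.8 and 2.4 participants.

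**4. Time at risk.** The share of the SoC column's time spent on SZC in hospital is d/(d + 187): 0.5%, 3.6% and 10.1% for 1, 7 and 21 days.

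**5. End of the window.** The 7-day rule does not say which last dose applies to Arm B. If it is the last in-hospital SZC dose, only about 7 outpatient days count. The SoC oedema figure becomes 1 − (1 − p0) × 0.983^(7/30) = 0.6%, 1.6% and 4.1%, of which 31%, 76% and 91% are run-in cases. Against 28.4%, 29.2% and 30.9% on SZC, the differences are 27.9, 27.6 and 26.9 points, larger than the outpatient 18.2. Time at risk would still run to study discontinuation.

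**6. Worst values.** By the Protocol's Schedule of Activities, the only scheduled visit at issue is discharge. It supplies one of three post-baseline dipsticks (discharge, 90, 180 days) and one of five post-baseline ECGs (discharge, 7, 90, 180 days, follow-up).

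**The case against.** **The Protocol also starts at first dose.** Protocol 9.4.4 defines treatment-emergent events from the first dose, so pooling the phases follows it. That is true of the definition, but it does not decide which events belong in a column headed SoC. SAP 4.6.2.1 separates the phases, and SAP 3.2 says what the SSR is for.

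**The information is available elsewhere.** SSO tables isolate inpatient events, listings show treatment at onset, and absolute event counts appear beside participant counts. These points stand in part. A later event after a run-in event is still in the absolute count. But run-in events add the same expected number to both arms' counts, which moves their ratio toward 1. The SSO is one pooled group, and a listing is not a comparison.

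**Some rows are hardly touched.** Deaths before randomisation cannot enter the SSR, and events that stopped treatment before randomisation hardly can. By-visit laboratory, vital-sign and ECG summaries do not pool phases. This stands.

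**The worst-value tables.** A reader might infer that the urinalysis and QTcF summaries also contradict SAP 3.2. The documents do not support that. SAP 3.3.1.2 ends the inpatient period before the randomisation date and starts the outpatient period on it, and the SAP 3.3.2 tables list Visit 3 among outpatient visits. The discharge value is therefore outpatient by the SAP's own rules. Protocol 9.4.4 also plans an overall worst value, although alongside one for each part of the study. What remains is minor: the discharge value is obtained on SZC in both arms.

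**Conclusion.** The inconsistency is real. As written, the SSR adverse event tables and event rate mix a common SZC run-in into an SZC versus SoC comparison, contrary to SAP 3.2. Taken alone, the early start pulls the arms' incidences together by the factor (1 − p0).

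The size is unknown because no document gives an in-hospital adverse event rate. It is small for rare terms and could be substantial for any adverse event if in-hospital events are common. The oedema illustration ignores acute illness and the higher correction dosing in hospital, so it fixes no upper limit. A reader might instead set the one-month risks of 5.2% and 1.7% against an assumed in-hospital incidence of 10% and see the ratio fall from 3.1 to 1.3. The documents give no basis for that 10%: the 10 g figure yields only 3.7% at 21 days.

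A reader might also infer that the tables understate the harm of continuing SZC. That is not established. If the 7-day rule is run from Arm B's last SZC dose, most SoC outpatient events drop out and the contrast is overstated against SZC. The net direction depends on a definition that the SAP does not give.

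Safety carries no hypothesis test and is reported descriptively, and no efficacy result is affected. This is a should-fix.

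**What to change.** In SAP 4.6.2.2:

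- Restrict the SSR adverse event tables to events with onset, or worsening in severity, on or after randomisation.
- Start SSR time at risk at randomisation.
- Use one end of window for both arms, tied to the end of the outpatient or follow-up period and not to the last SZC dose. Apply it to events and time at risk alike.

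Do not simply filter on the outpatient category in SAP 4.6.2.1. It ends 7 days after study treatment discontinuation and, if that is read as SZC, would leave Arm B about one week of events. That definition needs the same end date.

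Run-in events stay in the SSO tables, so nothing is lost. As a minor change, in SAP 4.6.4.2 and 4.6.7.2 take the SSR worst or maximum value from visits after discharge.

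The cost is SAP wording, a defined end date that also works for Arm B, and changes to table filters and denominators. No new data are needed. Protocol 9.4 requires SAP changes to be final before database lock.
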